### Primary Outcome: Speech recognition in two-talker masking speech

Perceptually Robust English Sentence Test Open-set (PRESTO) sentences (Tamati, Gilbert, and Pisoni 2013) will be presented in quiet and with a two-talker masker at an average target-to-masker ratio of +5 dB. Participants will hear lists 7 and 15 in quiet and 13 and 17 in noise, to limit the impact of cross-list differences in difficulty (Faulkner et al. 2015) on speech recognition accuracy. Performance will be quantified as the percentage of keywords correctly identified across sentences (152 keywords per condition).

For the two-talker masker, PRESTO sentences from unused sentence lists will be concatenated into a running speech stream. Two samples of this running stream will be sampled and superimposed to form the competing speech for each target sentence. Two talkers will be used to maximize the impact of informational masking on speech recognition (Freyman, Balakrishnan, and Helfer 2004). The masking speech will start 0.5 s prior to the target speech and stop 0.5 s after to ensure that participants are given a timing cue to distinguish the masker from the target. The combination of target sentence and maskers will be fixed (“frozen”) across participants to account for fluctuations in the amount of energetic masking that arise from interactions between targets and maskers (Buss et al. 2020). We will fix long-term target-to-masker ratio because that is conventional in speech recognition research. In addition, we will calculate short-term envelope ratio, defined as the proportion of time in which the target speech has a larger instantaneous envelope than the masker for each sentence.

#### Predictor 1: Auditory resolution

Preliminary data from 20 participants with cochlear implants tested in the lab indicates that spectral and temporal modulation detection thresholds predict PRESTO sentence recognition accuracy in quiet. In a generalized linear regression model, spectral and temporal modulation detection thresholds accounted for  $R^2 = 0.64$  of the variance in recognition accuracy (spectral  $\beta = -0.76$ , temporal  $\beta = -0.47$ ). We will repeat these tasks in this study.

Modulation detection thresholds will be measured with a three-interval, three-alternative forced-choice task. The carrier signal is a 60 dB SPL, 400 ms long noise burst with energy between 350 and 6500 Hz (selected to match the stimuli in Litvak et al. 2007), gated on and off with 20 ms  $\sin^2$  ramps. Carriers are modulated in the target interval and was unmodulated in the other two intervals. Feedback is given after each trial. In the temporal modulation detection task, the target interval is sinusoidally amplitude-modulated at a 100 Hz rate, which has been previously shown to correlate with speech recognition in listeners with cochlear implants when presented via direct stimulation (Fu 2002; Luo et al. 2008) and via a loudspeaker (Won et al. 2011). In the spectral modulation detection task, the target interval is spectrally modulated at 0.5 ripples per octave, which has been previously shown to correlate with speech recognition when presented via a loudspeaker (Anderson et al. 2012; Litvak et al. 2007; Saoji et al. 2009). Carrier level for every interval is randomly varied between -3 and +3 dB Sound Pressure Level (SPL) to diminish the availability of loudness differences between modulated and unmodulated intervals (McKay and Henshall 2010).

A 2-down, 1-up adaptive procedure will be used to measure modulation depth threshold, which converges on 71% detection accuracy (Levitt 1971). The temporal modulation detection task starts at a modulation depth of 100% and decreases in steps of 4 dB from the first to fourth reversal and 1 dB for the remaining reversals. The spectral modulation detection task starts at a peak-to-valley ratio of 40 dB and decreases in steps of 4 dB from the first to fourth reversal and 1 dB for the remaining reversals. Runs will end after 55 trials or 8 reversals. For each run, the final 4 reversals will be averaged to obtain the modulation threshold. Participants will complete three runs of each task. Outcomes will be the mean threshold across all runs of each task.

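### A spectral modulation run stopped at 55 trials with fewer than 8 reversals can be scored on its coarse starting reversals

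*Protocol*

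**What the plan says.** The rules are in the protocol under Predictor 1: Auditory resolution. The track is 2-down, 1-up. The spectral track "starts at a peak-to-valley ratio of 40 dB and decreases in steps of 4 dB from the first to fourth reversal and 1 dB" after that. The temporal task uses the same step sizes from 100% depth. Two stopping conditions apply, and one scoring rule covers every run: "Runs will end after 55 trials or 8 reversals. For each run, the final 4 reversals will be averaged to obtain the modulation threshold". Each participant does three runs per task, and "Outcomes will be the mean threshold across all runs of each task".

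The protocol sets no minimum number of reversals, does not require the scored reversals to come from the 1-dB phase, and has no rule to discard or repeat a capped run. The SAP uses the thresholds in Steps 2 and 3 and adds nothing on how they are scored.

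**The concern.** The scoring rule fits a run that ends on its eighth reversal: the last four are then reversals 5 to 8, all in the fine phase. It does not fit a run that ends on the trial count. Two early slips can use up all four coarse reversals while the level is still far above threshold. The track then descends only 1 dB for every two correct answers and can run out of trials before it turns again. The last four reversals are then the first four, and the score describes the start of the run rather than the listener.

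The error is mainly upward, and it falls on listeners with low thresholds, who are furthest from 40 dB. Spectral threshold is the stronger of the two auditory predictors in the preliminary model (beta = -0.76, against -0.47 for temporal) and enters the models in SAP Steps 2 and 3. With 30 participants, one badly scored run could produce an outlying predictor value.

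**Working it through.** **1. The plan's own figure.** A 2-down, 1-up track settles where two correct answers in a row have probability one half: p² = 0.5, so p = 0.7071. This matches the stated 71%.

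**2. Which reversals are scored.**
- 8 reversals: numbers 5-8, all fine.
- 7 reversals: numbers 4-7, one coarse.
- 6 reversals: numbers 3-6, two coarse.
- 5 reversals: numbers 2-5, three coarse.
- 4 reversals: numbers 1-4, all coarse.

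**3. Traced runs.** Inputs from the protocol: start 40 dB, 4-dB steps to the fourth reversal, then 1 dB, stop at 55 trials or 8 reversals. Assumptions: 4-dB steps before the first reversal, level not above 40 dB, and a listener who is correct at 10 dB or more except for the slips named. The text does not say whether the step made at the fourth reversal is 1 dB or 4 dB, so both readings are shown.

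| Slips on trials | First four reversals (dB) | Run score, 1-dB reading | Run score, 4-dB reading |
|---|---|---|---|
| none | 8, 12, 8, 12 | 9.5 | 9.25 |
| 3 and 8 | 36, 40, 32, 36 | 36 | 36 |
| 3 and 6 | 36, 40, 36, 40 | 38 | 38 |
| 5 and 10 | 32, 36, 28, 32 | 32 | 15 |
| 7 and 14 | 28, 32, 20, 24 | 9.5 | 9.5 |

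For slips on 3 and 8, the fourth reversal falls on trial 10 at 36 dB. The remaining 45 trials allow 22 downward steps of 1 dB. The level at trial 55 is therefore 35 - 22 = 13 dB, or 32 - 22 = 10 dB under the 4-dB reading. Neither is below 10 dB, so no fifth reversal occurs. The score is (36 + 40 + 32 + 36)/4 = 36 dB.

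**4. The analysed value is a three-run mean.** With two clean runs at 9.5 dB:
- one run at 36 dB: (36 + 9.5 + 9.5)/3 = 18.3 dB, a rise of 8.8 dB;
- one run at 38 dB: (38 + 9.5 + 9.5)/3 = 19.0 dB, a rise of 9.5 dB.

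**5. How many slip pairs do this.** Of the 45 possible pairs in trials 1-10, for true thresholds of 5-10 dB and the 1-dB reading, 33% give a run score of 30 dB or more and 18% give 36 dB or more. The median pair does no harm. At a true threshold of 20 dB, slips on 3 and 6 score correctly (19.5 dB).

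**6. How often, under assumptions.** Slip rates, psychometric slopes and true thresholds are not in the documents. With a three-alternative signal-detection model, a 6 dB threshold, two slopes and both step readings:

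| Assumed slip rate | Runs capped | Runs scoring 28 dB or more | Expected number of the latter in 30 × 3 = 90 runs, if every participant had a 6 dB threshold |
|---|---|---|---|
| 2% | about 1-4% | about 0.2-0.5% | 0.2-0.45 |
| 5% | about 3-6% | about 1-2% | 0.9-1.8 |

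A logistic model at a 5 dB threshold gave somewhat more capping (4-5% and 8-9% of runs) and similar rates of scores of 30 dB or more (about 0.5% and 2%). At 2% slips, roughly half of capped runs have 7 reversals and are only mildly biased (7.4-9.4 dB, against 6.5-7.7 dB for completed runs).

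**7. What excluding capped runs gains.** Three-run outcome at a true 5 dB (logistic model, slope 1.5 dB):

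| Assumed slip rate | All runs, mean (SD) | Completed runs only, mean (SD) |
|---|---|---|
| 0% | 5.55 (0.76) | 5.54 (0.77) |
| 2% | 6.16 (1.93) | 5.79 (1.14) |
| 5% | 8.28 (3.75) | 7.35 (3.19) |

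At 5% slips, exclusion removes 8.28 - 7.35 = 0.93 dB of a rise of 8.28 - 5.55 = 2.73 dB, about a third. Over an assumed population (mean 10, SD 4 dB), the correlation of score with true threshold rises by about 0.005-0.016 at 2% slips and 0.02-0.04 at 5%, and not at all without slips.

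**8. Temporal task.** Slips on 3 and 6 still give correct scores down to a true threshold of -20 dB. Under 1% of simulated temporal runs were affected.

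**The case against.** The strongest case against is that the harm is rare and diluted. Most slip pairs leave the score intact, the commonest capped run is only mildly biased, and the outcome averages three runs. The slip rates that drive the frequencies are assumed. Some examples depend on an unstated detail: slips on 5 and 10 give 32 dB or 15 dB according to the step at the fourth reversal. The preliminary thresholds already accounted for R² = 0.64 of the variance in 20 implant users, the tasks are to be repeated, and the study calls itself a pilot. Excluding capped runs also leaves most of the slip-related bias at a 5% slip rate.

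All of this stands as to size. It does not remove the defect: the rule as written returns 36 or 38 dB under either step reading in the cases above, and nothing elsewhere in the documents corrects it.

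A reader might infer that any good listener with two early slips receives a near-worst spectral threshold. That does not follow: the near-start value belongs to one run, and only for some slip timings. A reader might also infer that the regression results will be materially distorted. No change in a coefficient, in power or in a conclusion has been calculated, and the documents give no slip rate from which to calculate one.

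**Conclusion.** The point holds as a minor one. The stopping and scoring rules do not fit together for a run capped at 55 trials, and a spectral run can be scored wholly on reversals near the 40 dB start. That a capped run can score 36 or 38 dB follows from the written rule for the listener described. In such a case the participant's three-run mean is inflated by roughly 9-10 dB. The expected frequency rests on assumed slip rates, slopes and thresholds: at 2% slips, fewer than one badly scored run is expected among the 90 spectral runs, and at 5%, about one or two. Without slips there is nothing to gain, and the temporal task is little affected. The case for acting is that the correction is nearly free, and that fixing the rule beforehand avoids deciding about outlying runs after seeing them.

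**What to change.** Amend the scoring text under Predictor 1 in the protocol, or add it to the SAP:

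- Only reversals in the 1-dB phase, from the fifth onward, may enter a run's threshold.
- A run that ends at 55 trials with fewer than 8 reversals is left out of the participant's mean for that task. A cut-off of 7 reversals performs about the same and keeps nearly complete runs, scored on reversals 5-7.
- The number of such runs is reported for each participant and task.
- Where no run of a task is completed, average whatever 1-dB-phase reversals are available and flag the value. If there are none, treat the threshold as missing.

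The same edit could state which step size applies before the first reversal and at the fourth.

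The cost is a few sentences and no extra testing. A few thresholds will rest on two runs instead of three, and bias from slips within completed runs remains.

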#### Predictor 2: Working memory

Preliminary data in young adults with normal hearing (Bosen and Doria, in review) demonstrate a link between a three different memory tasks and recognition of vocoded speech in the presence of a speech masker. These results indicate that the ability of young adults with normal hearing to recognize vocoded speech in speech is sensitive to individual differences in storage and processing. Digit span is also associated with vocoded sentence recognition in quiet in individuals with normal hearing (Bosen and Barry 2020).

In contrast, we did not find a relationship between PRESTO sentence recognition accuracy in quiet and digit span performance in 20 listeners with cochlear implants after controlling for auditory resolution ( $r = 0.25$ ,  $p = 0.28$ ). This finding differs from results in young adults with normal hearing listening to vocoded speech, but additional working memory tasks are needed to determine the reason for this difference. In this study, we will use a battery of quick, reliable memory tasks which assess both storage and processing to determine their relative importance when listening in quiet and in competing speech. These tasks include the three tasks shown to be associated with vocoded speech recognition in competing speech:

*Reading Span* (primarily processing) – Participants alternate between judging if sentences are semantically sensible and storing letters in memory. Between 3 and 7 sentence-letter pairs are presented in each trial, after which participants recall the letters in order. The outcome is the total percentage of letters recalled in the correct position (Conway et al. 2005).

*Serial Digit Span* (primarily storage) – Participants hear a list of between 2 and 9 spoken digits presented with one second between stimulus onsets, then verbally repeat them in order (Bosen and Barry 2020; Bosen and Luckasen 2019). The outcome is the total percentage of digits recalled in the correct position.

*Free Recall* (primarily storage) – Participants read a list of 12 monosyllabic words shown for 750 ms with 250 ms between words, then repeat back words as they remember in any order. The outcome is the average number of words recalled from the list.

We will include a further two tasks to balance the distribution of tasks which primarily load onto storage and processing and to promote segregation of factors, because adding more measures facilitates latent factor identification (de Winter, Dodou, and Wieringa 2009). Digit updating is included to provide a task which primarily loads onto processing but does not require reading comprehension as reading span does. Running digit span requires both storage and processing (Shipstead et al. 2014) and also avoids linguistic variability.

*Digit Updating* (primarily processing) – Participants see between two and six boxes on screen. Sequences of digits are shown, one digit at a time, in a pseudorandom order across the boxes. Participants remember the most recent number shown in each box, and when the sequence ends, they must type in the last number that was shown in each box. The outcome is the percentage of last numbers correctly recalled across boxes. This task will be implemented as described in (Wilhelm, Hildebrandt, and Oberauer 2013).

*Running Digit Span* (storage and processing) – Between 12 and 20 spoken digits are presented at a rate of 4 per second, and participants recall as many digits as they can in order from the end of the list. The outcome is the average number of digits recalled in the correct position relative to the last item in the sequence across lists. This task will be implemented as described in (Cowan et al. 2005).

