## Study Protocol

### Objectives

Individuals with cochlear implants struggle to understand speech in the presence of competing sound sources, although there is a wide range of individual variability in speech recognition outcomes across individuals (e.g. Friesen et al. 2001; Stickney et al. 2004). This variability can be attributed to individual differences in the quality of the auditory input that the listener can hear (“bottom-up” factors) and the cognitive abilities of the listener which facilitate the extraction of meaningful information from that input (“top-down” factors).

In quiet conditions, these factors explain much of the individual differences between cochlear implant users. “Bottom up” constraints on auditory resolution, reflected in sensitivity to temporal (Fu 2002; Luo et al. 2008) and spectral (Litvak et al. 2007; Saoji et al. 2009) modulations in acoustic signals, account for about half of the variance in cochlear implant listeners’ speech recognition accuracy in quiet (Won et al. 2011). “Top down” cognitive measures believed to reflect individual differences in attention and fluid intelligence have also been linked to cochlear implant users’ sentence recognition in quiet (e.g. Moberly and Reed 2019).

Interpreting the meaning of correlations between speech recognition and tests of cognitive function is challenging because individual differences in most cognitive tasks have a positive association with one another (Diamond 2013; Miyake and Friedman 2012; Shipstead et al. 2014) and with speech recognition (Dryden et al. 2017). The challenge in interpretation is that previously observed correlations may not arise from a direct relationship between a measured cognitive skill and speech recognition, but rather from an incidental link via some intermediate cognitive skill which is related to both the measured skill and speech recognition. Thus, it is possible that the use of isolated memory tasks (as in previous studies) fails to measure the critical individual differences that govern speech recognition in quiet and in noise. To address this limitation of previous work, this proposal includes a battery of working memory tasks designed to assess individual differences in the ability to store and process information in memory while minimizing confounds that arise from task-specific individual differences.

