### Step 2: Predict speech recognition accuracy in quiet

We expect both modulation detection thresholds to be significant predictors of sentence recognition accuracy, which will account for approximately half of the variance. We will compare the likelihood of generalized linear regression models which include only modulation detection thresholds against models which also include the memory components identified in step 1 to determine if these memory components are significant predictors of speech recognition in quiet. We will verify that modulation detection thresholds and working memory task performance are not correlated, as we found in participants with cochlear implants ( $r = -0.36$ ,  $r = -0.15$  for spectral and temporal threshold correlations with digit span,  $p > 0.10$ ).

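### Two of the five memory tasks are heard through the implant, so the memory components can carry hearing that the thresholds miss; the SAP needs a visual-only sensitivity analysis

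*Protocol*

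**What the plan says.** The Protocol's Objectives set out to separate bottom-up hearing from top-down cognition, with a memory battery aimed at "minimizing confounds that arise from task-specific individual differences". The section Predictor 2: Working memory describes five tasks.

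- Serial digit span is heard: "Participants hear a list of between 2 and 9 spoken digits presented with one second between stimulus onsets".
- Running digit span is heard at a faster rate: "Between 12 and 20 spoken digits are presented at a rate of 4 per second, and participants recall as many digits as they can".
- Free recall is read: "Participants read a list of 12 monosyllabic words shown for 750 ms with 250 ms between words".
- Digit updating is visual: "Participants see between two and six boxes on screen".
- Reading span is a reading task. Digit updating was added as "a task which primarily loads onto processing but does not require reading comprehension as reading span does".

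Participants listen with their everyday implant configuration (Protocol, Participants). SAP Step 1 enters all five scores into one principal components analysis and carries forward every component with an eigenvalue above one. SAP Step 2 compares a model containing only the modulation thresholds with one that adds these components. It also plans to verify that thresholds and memory scores are uncorrelated, citing pilot values of r = -0.36 and r = -0.15 "for spectral and temporal threshold correlations with digit span".

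The section Predictor 3: stream segregation states that identifying digits does not depend on auditory resolution. It says so of a task with one digit every 0.5 s.

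**The concern.** In the two spoken tasks, the score cannot tell a digit that was misheard from one that was forgotten. Hearing quality can therefore enter the memory components. If the two modulation thresholds do not capture all of hearing quality, a memory component can add to the prediction of speech recognition because it stands in for the remainder. At stake are the Step 2 conclusion on memory in quiet and the memory paths in Step 3.

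Modality also partly overlaps the contrast between storage and processing that the battery is meant to examine. A component that separates spoken from visual tasks could be mislabelled as storage versus processing.

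**Working it through.** **Presentation rates.** Running span: 1/4 = 0.25 s per digit. Stream segregation: 0.5 s. Serial span: 1 s. Running span is thus twice as fast as the task for which the protocol claims digits are insensitive to hearing, and four times as fast as serial span. No section supports the claim at 0.25 s.

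**Pilot correlations (n = 20; pilot digit span taken to be the spoken task).** For r = -0.36, |t| = 0.36 × √18 / √(1 - 0.36²) = 1.64, so p = 0.12. The 95% interval is tanh(-0.377 ± 1.960/√17) = -0.69 to 0.10. For r = -0.15, p = 0.53, interval -0.56 to 0.31. The SAP's statement that p exceeds 0.10 is reproduced. Neither interval shows absence of correlation.

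**Planned check (n = 30).** The same Fisher z method returns the protocol's 29 participants for r = 0.5: ((1.960 + 0.842)/0.549)² + 3 = 29.01.

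- Critical |r| = 2.048/√(28 + 2.048²) = 0.361. A repeat of the pilot's 0.36 would be read as not correlated.
- Power at |r| = 0.36: Φ(0.377 × √27 - 1.960) = Φ(-0.002) ≈ 50%.
- Participants for 80% power: (2.802/0.377)² + 3 ≈ 58.3, so 59.

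**What threshold adjustment leaves.** The pilot R² of 0.64 for quiet speech leaves 1 - 0.64 = 36% unexplained; the SAP expects the thresholds to explain about half. The documents do not say how much of the remainder is hearing.

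**Simulation.** From the documents: n = 30, inter-task correlation 0.3, eigenvalue rule, adjustment for two thresholds, alpha 0.05. Assumed: no true memory effect, hearing explains 80% of quiet accuracy, normal outcomes, F test, and spoken tasks correlating 0.36 with the main threshold. With reliability *rel*, the implied correlation with hearing itself is 0.36/√rel: 0.46, 0.42 and 0.38 at 0.6, 0.75 and 0.9. The main threshold then explains 0.8 × rel = 0.48, 0.60 and 0.72 of quiet accuracy.

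| False-positive rate, memory components | rel 0.6 | rel 0.75 | rel 0.9 |
|---|---|---|---|
| Both spoken tasks affected | about 19% | about 10% | about 5% |
| Running span only | about 9% | about 7% | about 5% |
| Visual tasks only | about 5% | about 5% | about 5% |

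One repeat gave 16% in place of 19%; other cells moved by about a point. A separate set-up fixed the correlation with hearing itself at 0.36 for both spoken tasks. It gave 4%, 7% and 13% when the two thresholds jointly capture 100%, 80% and 60% of hearing. A likelihood-ratio chi-square test runs at about 8% at this sample size even with no leak. That is a separate small-sample effect, so F-test rates are shown.

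**Second component.** With a hearing loading of 0.36 on both spoken tasks, they correlate 0.3 + 0.36² = 0.43 with each other. The population eigenvalues are 2.25, 0.78, 0.70, 0.70 and 0.57. The second contrasts spoken with visual tasks. It lies below one, yet at n = 30 a second component is kept in about 57% of samples through sampling variation.

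**Overlap of modality and construct.** Order: reading span, serial span, free recall, updating, running span. Code storage 0, 1, 1, 0, 0.5 ("Running digit span requires both storage and processing") and spoken 0, 1, 0, 0, 1. The correlation is 0.5/√(1.0 × 1.2) = 0.46, a partial overlap.

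**The case against.** The plan is not silent on hearing. It argues that digits are easy to identify, adjusts for thresholds and plans a correlation check. Hearing that the thresholds capture does not inflate the memory test: the simulated rate is 4 to 5% when they capture all of it. The pilot's r = -0.36 is compatible with zero, and a shared cause such as age could give the same sign in a sample aged up to 80. In the pilot, digit span did not predict quiet accuracy after control for auditory resolution (r = 0.25, p = 0.28), so the feared route did not appear there. The plan's digit argument reasonably covers serial span, which leaves running span as the main gap.

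Most of this stands, and it limits the size of the point. It does not remove it: 20 pilot participants settle neither question, and the documents report no pilot data for running span.

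A reader might infer that the memory components are in fact measuring hearing, or that the error rate is very high. The documents support neither. A correlation of 0.5 would give rates up to 38% at reliability 0.6, but nothing in the documents points to 0.5. A reader might also infer that storage and processing are fully confounded with modality; free recall, a visual storage task, prevents that.

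**Conclusion.** The point holds as a risk to interpretation that the planned safeguards do not close. If the thresholds explain quiet speech as well as in the pilot (R² = 0.64, with hearing explaining 80%), the false-positive rate with both spoken tasks affected is about 8%. It approaches 15 to 19% only if they explain about half, as the SAP expects. If running span alone is affected, the range is about 5 to 9%. These figures rest on the assumed correlation of 0.36, the assumed reliabilities of 0.6 to 0.9 and the assumed 80%. The firm findings are that two of five tasks are spoken, that running span exceeds the rate at which the plan defends digits, and that the Step 2 check has no criterion or consequence and would pass the pilot's own value.

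**What to change.** In the SAP:

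- Keep the five-task components as the main analysis and report the loadings of each retained component by modality.
- Pre-specify a sensitivity analysis that repeats Steps 2 and 3 with components from reading span, free recall and digit updating only. Standardise component scores so that coefficients are comparable, and report estimates with confidence intervals.
- State that a memory effect that is clearly smaller or absent in the visual-only estimate will be described as not separable from hearing. Judge this on the estimate and its interval, not on significance.
- State that a second component separating spoken from visual tasks will not be labelled storage versus processing.

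Do not require statements on storage versus processing to replicate in the visual-only set. It has one storage task, its expected eigenvalues are 1 + 2 × 0.3 = 1.6, 0.7 and 0.7, and it keeps a second component in only about 11 to 12% of samples. Such a rule would usually block the comparison whether or not hearing had leaked in.

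The cost is SAP wording and one extra model run on data already planned. The three-task memory measure is less precise than the five-task one, so both results should be shown.
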